6.4 Reporting Requirements for Safety Parameters

6.4.1 Study Reporting Period and Follow-up for Adverse Events

The reporting period for AEs is the period immediately following the time that written informed consent is obtained until the end of subject participation in the study.

Nonserious AEs will only be captured during the first year of the subject's participation in the study, but will be followed to resolution until the end of subject participation in the study. Nonserious AEs that result in interruption of investigational product and/or discontinuation from the study will be captured at any time during the subject's participation in the study.

6.4.2 Reporting of Serious Adverse Events

6.4.2.1 Study Reporting Period and Follow-up for Serious Adverse Events

The reporting period for SAEs is the period immediately following the time that written informed consent is obtained through the end of subject participation in the study. After submitting an initial SAE report for a subject (to MedImmune Patient Safety), the investigator is required to follow the subject proactively and provide further information on the subject's condition to MedImmune Patient Safety.

At any time after completion of the study, if an investigator or qualified designee becomes aware of an SAE that is suspected by the investigator or qualified designee to be related to investigational product, the event must be reported to MedImmune Patient Safety.

The investigator is responsible for following all SAEs until resolution, until the subject returns to baseline status, or until the condition has stabilized with the expectation that it will remain chronic, even if this extends beyond study participation.

6.4.2.2 Notifying the Sponsor of Serious Adverse Events

Within 24 hours of identifying an SAE, regardless of the presumed relationship to the investigational product, the investigator or qualified designee must complete the SAE Report Form and fax it to MedImmune Patient Safety.

MedImmune contact information:

Patient Safety MedImmune [name] [contact]

The sponsor is responsible for reporting certain SAEs as expedited safety reports to applicable regulatory authorities, ethics committees, and participating investigators, in accordance with ICH Guidelines and/or local regulatory requirements (see Section 6.4.2.3). The sponsor may be required to report certain SAEs to regulatory authorities within 7 calendar days of being notified about the event; therefore, it is important that investigators submit additional information requested by the sponsor as soon as it becomes available.

Investigators should provide all available information at the time of SAE Report Form completion. Investigators should not wait to collect additional information to fully document the event before notifying MedImmune Patient Safety of an SAE. When additional

information becomes available, investigators should submit a follow-up SAE Report Form (separate from the initial report form) with the new information. Any follow-up information to an SAE also needs to be provided to MedImmune Patient Safety within 24 hours of learning of the new information.

6.4.2.3 Safety Reporting to Investigators, Institutional Review Boards or Independent Ethics Committees, and Regulatory Authorities

The sponsor is responsible for reporting all applicable SAEs to regulatory authorities, investigators, and IRBs/IECs, as applicable, in accordance with national regulations in the countries where the study is conducted. The sponsor will also prepare an expedited report for other safety issues where these might materially alter the current risk/benefit assessment of an investigational product or that would be sufficient to consider changes in the administration of the investigational product or in the overall conduct of the study.

For all investigators located in the European Economic Area, the sponsor will be responsible for reporting suspected unexpected serious adverse reactions (SUSARs) and any other applicable SAEs to regulatory authorities including the European Medicines Agency (EMA), investigators, and IRBs/IECs, as applicable, in accordance with national regulations in the countries where the study is conducted. The SUSARs will be submitted within 7 days for fatal and life-threatening events and within 15 days for other serious events, unless otherwise required by national regulations.

For all other investigators, the sponsor will prepare an expedited report for all SAEs that are unexpected and potentially related to the investigational product, and copies will be distributed to all concerned regulatory authorities, investigator(s), and IRBs/IECs according to applicable laws and regulations. The investigational site also will forward a copy of all expedited reports to the site's applicable IRB/IEC. Investigators must also submit safety information provided by the sponsor to the IRB/IEC as detailed in Section 10.1 and Section 10.2.

6.4.3 Other Events Requiring Immediate Reporting

6.4.3.1 Overdose

An overdose is defined as a subject receiving a dose of investigational product in excess of that specified in the IB, unless otherwise specified in this protocol.

Any overdose of a study subject with the investigational product, with or without associated AEs/SAEs, is required to be reported within 24 hours of knowledge of the event to MedImmune Patient Safety using the Safety Fax Notification Form (see Section 6.4.2.2 for

contact information). If the overdose results in an AE, the AE must also be recorded on the AE CRF (see Section 6.3.1). Overdose does not automatically make an AE serious, but if the consequences of the overdose are serious, for example death or hospitalization, the event is serious and must be reported as an SAE (see Section 6.3.1 and Section 6.4.2).

6.4.3.2 Hepatic Function Abnormality

Hepatic function abnormality (as defined in Section 6.1.3) of unknown etiology, or which is considered attributable to investigational product, is required to be reported as "hepatic function abnormal" *within 24 hours of knowledge of the event* to MedImmune Patient Safety using the SAE Report Form, even if the event is considered to be nonserious (see Section 6.4.2.2 for contact information). The investigator will review the data with the medical monitor. The investigator should then use clinical judgment to establish the cause based on local SOC and follow the subject by conducting testing as clinically indicated:

- If, after appropriate workup, in the opinion of the investigator, the underlying diagnosis for the abnormality remains unexplained, or is considered attributable to investigational product, dosing of the study subject should be discontinued.
- If ALT or AST is greater than 3 × ULN please refer to Guidance for Abnormal Liver Function Tests Management in Appendix 8.

Each reported event of hepatic function abnormality will be followed by the investigator and evaluated by the sponsor. If the etiology of the event remains unconfirmed and/or is considered related to investigational product (see Section 6.2.2.1), a prompt cumulative review of safety data and the circumstances of the event in question will be conducted and assessed by a MedImmune safety review committee (see Section 6.5) to determine whether continued dosing of current study subjects and/or study entry should be interrupted, whether the protocol will be modified, or whether the study will be discontinued permanently. Review and approval by the committee is required for resumption of subject dosing or study entry in the event that the study is interrupted. Where applicable, regulatory authorities and IRBs/IECs will be notified of any actions taken with the study.

6.4.3.3 Pregnancy

Pregnancy in a female subject who has received investigational product is required to be reported *within 24 hours of knowledge of the event* to MedImmune Patient Safety or designee using the Safety Fax Notification Form (see Section 6.4.2.2 for contact information).

Subjects who become pregnant during the study period must not receive additional doses of investigational product and will be withdrawn from the study. After obtaining the subject's consent, the pregnancy will be followed for outcome of the mother and child (including any premature terminations) and should be reported to MedImmune Patient Safety after outcome.

Should the investigator become aware of a pregnancy in the partner of a male study subject who has received investigational product this should be reported *within 24 hours of knowledge of the event* to MedImmune Patient Safety using the Safety Fax Notification Form (see Section 6.4.2.2 for contact information). The sponsor will endeavor to collect follow-up information on such pregnancies provided the partner of the study subject provides consent.

6.5 Safety Management During the Study

The MedImmune medical monitor has primary responsibility for the ongoing medical review of safety data throughout the study. This includes review of SAEs and timely review of AEs and "other events" reported during the study. MedImmune Patient Safety is responsible for the receipt, immediate review, investigation, and follow-up of SAEs and other immediately reportable events (eg, overdose and pregnancies) reported from the clinical study sites.

A MedImmune safety review committee provides safety surveillance, guidance, and oversight for all clinical development studies in which MedImmune has sponsor accountabilities. The Committee is chaired by the Clinical Medical Director and includes appropriate representatives from Patient Safety, Pre-Clinical Development, and Regulatory Affairs. The committee reviews protocol and program-specific safety data and assessed changes to the benefit/risk profile of the molecule during early phases of development. Based on review of safety data, the committee may suspend enrollment or subject dosing in clinical studies, request modification of study documents, or take other actions as deemed necessary.

An independent DSMB is an advisory to the sponsor and will perform evaluations of safety data at specified time points throughout the study in accordance with the DSMB Charter and make recommendations to the sponsor regarding the conduct of the study (see Section 7.6).

7 STATISTICAL CONSIDERATIONS

7.1 General Considerations

Data will be provided in data listings sorted by SID number. Categorical data will be summarized by the number and percentage of subjects in each category. Continuous variables will be summarized by descriptive statistics, including mean, standard deviation, median, minimum, and maximum. Baseline will be defined as the Day 1 value of this OLE study prior to investigational product administration. Details of endpoint analyses will be described in the Statistical Analysis Plan.

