1.2.1 Product Derivation

1.2.2 Summary of Nonclinical Experience

1.2.3 Summary of Clinical Experience

MEDI-546 has been or is being investigated in 4 MedImmune/AstraZeneca-sponsored clinical studies in adult subjects with systemic sclerosis (SSc) or SLE. One study in SSc is complete (Study MI-CP180) and 3 studies in SLE, including the current study, are ongoing (Studies CD-IA-MEDI-546-1013, CD-IA-MEDI-546-1145, and D3461C00002).

Study CD-IA-MEDI-546-1013, a Phase 2b, randomized, double-blind, placebo-controlled, parallel-group study to evaluate the efficacy and safety of MEDI-546 in adult subjects with chronic, moderately-to-severely active SLE with an inadequate response to standard of care treatment for SLE, is currently ongoing and remains blinded. Enrollment in this study is complete. An interim analysis was conducted after the 210th randomized subject completed the Day 169 visit or discontinued from study treatment early. A total of 307 subjects have been randomized in a 1:1:1 ratio to receive a fixed IV dose of MEDI-546 (300 or 1000 mg) or placebo every 4 weeks (Q4W) for 48 weeks on Days 1, 29, 57, 85, 113, 141, 169, 197, 225, 253, 281, 309 and 337 for a total of 13 doses. There is an 85-day follow-up period in Study CD-IA-MEDI-546-1013, which the subjects must complete to be considered for enrollment into Study CD-IA-MEDI-546-1145.

Study D3461C00002, a Phase 2, multicenter, open-label, dose-escalation study to evaluate the safety and tolerability of MEDI-546 in adult Japanese subjects with active SLE, is

currently ongoing. Enrollment in this study is complete. A total of 17 subjects are receiving a fixed IV dose of MEDI-546 (100, 300, or 1000 mg) Q4W for 48 weeks for a total of 13 doses followed by a fixed IV dose of MEDI-546 (300 or 1000 mg) Q4W for 104 weeks for a total of 27 doses.

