2.3 Exploratory Objectives

3 STUDY DESIGN

3.1 Overview of Study Design

This is an open-label, multinational, multicenter study to evaluate the long-term safety and tolerability of MEDI-546 in adult subjects with chronic, moderately-to-severely active SLE who were previously treated with investigational product (MEDI-546 or placebo) and completed Study CD-IA-MEDI-546-1013 through treatment and follow-up. The study will be conducted in approximately 240 subjects at up to 100 study sites.

Once subjects have completed treatment and follow-up in Study CD-IA-MEDI-546-1013 (through Day 422), signed the informed consent form (ICF), and met all study eligibility criteria, they may be enrolled in this OLE study. The start of this OLE study (defined as the day [Day 1] the subject receives their first dose of open-label MEDI-546) should occur within 28 days of the Day 422 visit of Study CD-IA-MEDI-546-1013 (with the exception of those subjects in the regions of Donetsk and Lugansk in the Ukraine, where the political situation necessitated a suspension of study activities) or at the discretion of the medical monitor if the start of this OLE study occurs outside the 28-day window. All subjects will receive IV MEDI-546 as a 300 mg fixed dose administered as an IV infusion over at least 30 minutes Q4W starting at Day 1 (Week 0) for up to 3 years or until the sponsor discontinues development of MEDI-546 for SLE, whichever comes first. All subjects will be followed for 85 days after receiving their last dose of MEDI-546.

At every visit, the investigator will evaluate the subject's clinical status and perform a risk/benefit analysis based on clinical judgment to determine if the subject should continue to receive MEDI-546 in the study.

Figure 3.1-1 Study Flow Diagram

IV = intravenous

The endpoints to be measured in this study are described in Section 7.3.

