3 STATISTICAL METHODS

3.1 General Considerations

Categorical data will be summarized by the number and percentage of subjects in each category. Continuous variables will be summarized by descriptive statistics, including mean, standard deviation, median, minimum, and maximum. Data will be provided in data listings sorted by treatment group and subject identification (SID) number.

Baseline will be defined as the last non-missing observation on or before Day 1 prior to investigational product administration of study CD1145.

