3.8.5 Clinical Laboratory Evaluation

Hematology, serum chemistry, lipid profile (HDL, LDL, cholesterol, and triglycerides), and urinalysis parameters will be collected in this study. The hematology, serum chemistry, and lipid profile parameters as well as their changes from baseline will be summarized with descriptive statistics by visit. The shift from baseline in hematology, serum chemistry, lipid profile, and urinalysis parameters will be summarized by visit.

Treatment-emergent laboratory/vital signs changes (TELVC) will be defined for post-baseline values according to the reference ranges given in **Appendix E**. Number of subjects with TELVC will be summarized by visit.

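### Change and shift tables start from OLE Day 1, which for an expected two-thirds of subjects follows 13 parent-study anifrolumab doses; split them by parent arm and add a pre-drug reference

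*Protocol*

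**What the plan says.** **Baseline.** Protocol 7.1: "Baseline will be defined as the Day 1 value of this OLE study prior to investigational product administration". SAP 3.1: "Baseline will be defined as the last non-missing observation on or before Day 1 prior to investigational product administration of study CD1145". The two agree when a Day 1 value exists. When it does not, the SAP reaches back to an older value and the protocol has none.

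**Prior exposure.** Protocol 1.2.3 says of the parent study that "307 subjects have been randomized in a 1:1:1 ratio to receive a fixed IV dose of MEDI-546 (300 or 1000 mg) or placebo", with the dosing days ending "197, 225, 253, 281, 309 and 337 for a total of 13 doses". It adds: "There is an 85-day follow-up period in Study CD-IA-MEDI-546-1013, which the subjects must complete to be considered for enrollment". Under Protocol 3.1 the first OLE dose "should occur within 28 days of the Day 422 visit of Study CD-IA-MEDI-546-1013". The medical monitor may allow a later start, and subjects from two Ukrainian regions are excepted.

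**Use of baseline.** SAP 3.8.5: "The hematology, serum chemistry, and lipid profile parameters as well as their changes from baseline will be summarized with descriptive statistics by visit". The same section plans laboratory shift tables, including urinalysis. Changes are also planned for vital signs (SAP 3.8.6.1) and immunoglobulins (SAP 3.7.1), and shifts for ECG (SAP 3.8.6.2) and ANA/ENA (SAP 3.7.1).

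**Grouping.** SAP 3.2.2 uses a single Anifrolumab Total group everywhere except the exposure-adjusted adverse-event rates. Those are split by OLE dose, not by parent-study arm.

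**The concern.** For subjects from the two active parent arms, the OLE Day 1 value was taken after treatment. Any effect that lasts through the off-drug interval is already in the baseline, so a change from it describes re-treatment and not change since before the drug. For ex-placebo subjects the same column does describe change since before the drug. Pooling the two gives a mean that answers neither question.

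The study's objective is long-term safety, and the ex-anifrolumab subjects carry the longest cumulative exposure. No planned change table shows how far their laboratory values, vital signs or immunoglobulins have moved since before their first dose. A slow drift across both studies could be hidden, and a return to drug after an off-drug rebound could look larger than it is.

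**Working it through.** **1. The plan's own figure.** SAP 2.4: 307 × (1 − 0.20) = 245.6, stated as approximately 240. Reproduced to within rounding.

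**2. Share previously on active drug.** Under 1:1:1 allocation and equal completion by arm the share is 2/3, and 240 × 2/3 = 160. The 20% loss is not split by arm, so take about 205 active and 102 placebo subjects as randomised and vary it:

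| Loss, active | Loss, placebo | Ex-anifrolumab share |
|---|---|---|
| 30% | 0% | 143.5 / 245.5 = 58.5% |
| 20% | 20% | 164.0 / 245.6 = 66.8% |
| 10% | 40% | 184.5 / 245.7 = 75.1% |

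The arithmetic limits with 240 completers are (240 − 102)/240 = 57.5% and 205/240 = 85.4%.

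**3. Time off drug at baseline.** The last scheduled parent dose is on Day 337. OLE Day 1 normally falls on parent Day 422 to 422 + 28 = 450.
- 422 − 337 = 85 days; 450 − 337 = 113 days.
- The Day 1 ECG is normally the parent Day 396 tracing (Protocol 5.1.2.1): 396 − 337 = 59 days.

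**4. Effect on a pooled mean change.** Let Δ be the drug effect at steady state and r the fraction of it still present at OLE Day 1. Assume one r for both parent doses and the same Δ on re-treatment.
- Ex-placebo change: Δ.
- Ex-anifrolumab change: (1 − r)Δ.
- Pooled change / Δ = 1/3 + (2/3)(1 − r) = 1 − 2r/3. For a general share s, it is 1 − s·r.

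| r | s = 0.575 | s = 2/3 | s = 0.854 |
|---|---|---|---|
| −0.25 (rebound) | 1.14 | 1.17 | 1.21 |
| 0 | 1.00 | 1.00 | 1.00 |
| 0.10 | 0.94 | 0.93 | 0.92 |
| 0.25 | 0.86 | 0.83 | 0.79 |
| 0.50 | 0.71 | 0.67 | 0.57 |
| 1 | 0.43 | 0.33 | 0.15 |

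No value of r is given in the documents, so the table shows a range and not an estimate. The formula applies to mean changes, not to shift tables.

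**5. TELVC.** Counting each threshold in SAP Appendix E gives 56 laboratory criteria over 28 parameters. Six use baseline: one each for haemoglobin, haematocrit, neutrophils and platelets, and two for albumin. The other 50 are absolute. Appendix F has 12 vital-sign criteria. Six use baseline, but each repeats the limit of a stand-alone criterion for the same variable, so an out-of-range value counts whatever the baseline.

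An invented example for one of the six (neutrophils, 10⁹/L): 2.0 before the drug, 1.2 at OLE Day 1, 0.9 in the OLE. The rules are below 0.5, or below 1.0 with a fall of at least 0.5. From OLE Day 1 the fall is 1.2 − 0.9 = 0.3, not flagged. From the pre-drug value it is 2.0 − 0.9 = 1.1, flagged.

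**6. Lipids.** Protocol Table 5.1-1 and 5.1.2.1 schedule no lipid sample on OLE Day 1; the first is at Week 4, after dosing has begun. The lipid change table therefore has no baseline under Protocol 7.1. Under SAP 3.1 it has one only if a parent-study value is carried in.

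**The case against.** The best defence is that OLE Day 1 is the natural baseline for an extension, that subjects have then been off drug for about three to four dosing intervals, and that the placebo-controlled parent study is the place to read the first-year effect. Actual values by visit are also summarised, so the data are not hidden altogether. This stands as a reason to keep OLE Day 1. It does not supply the missing contrast, because the actual values too are planned for one pooled group and no summary of pre-drug parent values is stated.

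A reader might go further in several ways that the documents do not support:

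- **That the plan will understate long-term change.** This requires r above 0. Full washout gives no distortion, and rebound gives an overstatement.
- **That the primary safety result is distorted.** TEAEs and TESAEs are the primary assessment (Protocol 7.3.1), and treatment emergence is defined by receipt of product (Protocol 6.1.1), not by a baseline measurement.
- **That TELVC flags fail in general.** Only the six laboratory criteria counted above are exposed.
- **That weight change and 21-gene neutralization are biased.** No weight-change table is stated, and SAP 3.6.1 does not give the reference for neutralization.
- **That a pre-drug baseline should replace OLE Day 1.** In a pooled table this would mix elapsed times. OLE Day 1 falls 421 to 449 days after parent Day 1. OLE Week 48 (336 days) is then 757 to 785 days from baseline for ex-anifrolumab subjects, against 336 for ex-placebo subjects.

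One further caution stands. The corticosteroid rule in Protocol 4.2.3 and 4.5.2 refers to the Study 1013 baseline, but that concerns steroid use. It does not show that comparable parent values exist for every laboratory or immunoglobulin variable.

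**Conclusion.** The point holds for the supporting descriptive tables. The planned laboratory, vital-sign and immunoglobulin changes, the laboratory, ECG and ANA/ENA shifts, and six laboratory TELVC criteria are referred to a value that is post-treatment for an expected two-thirds of subjects. They are pooled with subjects for whom it is not. These summaries can misstate change since before the drug. For mean changes, the ratio runs from 1.00 with no persistence to 0.33 with full persistence, and exceeds 1 under rebound. This rests on equal completion by arm, a single r, and the same steady-state effect on re-treatment, none of which the documents establish. Direction and size are therefore unknown, and the plan as written gives no means of finding out. It is an inexpensive improvement worth making, not a flaw in the primary safety summaries.

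**What to change.** 1. Keep OLE Day 1 as the baseline.
2. In SAP 3.1 and 3.2.2, present the change tables, the shift tables and the six baseline-dependent laboratory TELVC criteria by parent-study arm (placebo versus anifrolumab).
3. For ex-anifrolumab subjects, add the same summaries from the last Study 1013 value before the first-ever anifrolumab dose, where a comparable parent value exists. Label them with time since that dose and do not pool them with ex-placebo subjects.
4. Give Protocol 7.1 and SAP 3.1 the same baseline definition, including what applies when the Day 1 value is missing.
5. State the source of the lipid baseline.

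The cost is SAP wording, a merge with parent-study data and a second set of tables, with no new visits or samples. The added ex-anifrolumab summaries will also contain any secular change over the parent period, such as disease course or background medication, and should carry a note saying so.
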